12.2 Adverse Event and Device Effect Definitions

The principal measures of safety will be the incidence of adverse events reported during the study. Adverse events will be collected until the subject has exited/withdrawn from the study. Only treatment-emergent adverse event will be collected and reported.

Examples of anticipated adverse events are:

- Temporary and mild, mouth or tongue sensations such as:
 - Numbness
 - Burning sensation
 - Tingling sensations
 - Taste alteration

The following are definitions related to safety:

Adverse event (AE) means any undesirable clinical occurrence in a patient, whether or not it is considered to be device- or drug-related.

Device-related adverse event (i.e., adverse device effect) is an AE considered by the Investigator to have a reasonable likelihood of being associated with the experimental device or device under study.

Serious adverse event is an adverse event or suspected adverse reaction which, in the view of either the investigator or sponsor, results in any of the following outcomes: Death, a threat to life, inpatient hospitalization or prolongation of existing hospitalization, a persistent or significant incapacity or substantial disruption of the ability to conduct normal life functions, or a congenital anomaly/birth defect. Important medical events that may not result in death, be life- threatening, or require hospitalization may be considered serious when, based upon appropriate medical judgment, they may expose the patient to an increased risk of such outcomes and may require medical or surgical intervention to prevent one of the outcomes listed in this definition.

Serious adverse device effect is a device effect that has a serious adverse effect on the health or safety of study participants, causing hospitalization , or is life threatening or causes death.

Unanticipated adverse device effect is any serious adverse device effect on the health or safety of study participants or any life-threatening problem or death, that is caused by or associated with a device. That effect, problem or death and its nature, severity or degree of incidence was not previously identified in the investigational plan or application. This also included any other unanticipated serious problem which may be associated with a device and is related to the rights, safety and welfare of patients.

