4 INTRODUCTION

4.1 Background and Rationale

Xerostomia is a common oral health problem, affecting up to 50% of the population (Furness et al. 2011). Xerostomia is a subjective feeling of dryness of the mouth and can present with or without reduced saliva production (Furness et al. 2011, Villa et al. 2015, Jose et al. 2016). Dry mouth may be associated with other conditions such as diabetes and hypertension. Dry mouth is also a common side effect of many different drugs, such as anti-hypertensives, anti-depressants, decongestants (Tan et al. 2018).

Mouth dryness is commonly associated with other symptoms such as taste disturbances, bad breath and painful mouth ulcers. Dry mouth may also affect speech, chewing and swallowing (Dawes 1987, Furuta et al. 2013).

Current management strategies include symptom relieving measures such as topical saliva substitutes, oral moisturizers, saliva stimulants, and also frequent sips of water. However, the evidence in favour of any particular topical therapy was weak (Jose et al. 2016, Villa et al. 2015). Other products (e.g., Biotène®, Hydris™) have became available for treating dry mouth in recent years, but there is an increasing demand for more effective dry-mouth relief products.

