The seventh visit should occur 35 (\pm 2) days after the baseline visit and could last up to 4 hours as it will collect all the pre-use and post-use information at multiple timepoints (5 min, 30 min, 60 min, 120 min, 240 min).

Before starting any treatment, the following pre-use measurements must be assessed by the Investigator or designated study staff:

- Visual Analogue Scale (VAS)
- Dry Mouth Relief Questionnaire (DMRQ)
- Oral Tissue Exam using the Challacombe Scale Score
- Intra-Oral Photo

Before starting any treatment, the following pre-use measurement must be completed by the patient:

- PPAQ4 (Questions 15 -23; completed while patient is in clinic)
- Dry Mouth Inventory (DMI)

Patients will not be allowed to eat or drink during the study visit except for when directed by study staff.

The patient will then self-administer the first dose of the treatment into their mouth using the second sample assigned.

The **post-use measurements** will include the following at the appropriate timepoints:

- 5 (+ 5) minutes after 1st dose: PPAQ1 (Questions 1-3; completed while patient is in clinic)
- 30 (± 10) minutes after 1st dose: PPAQ2 (Questions 1-11; completed while patient is in clinic)
- 60 (± 10) minutes after 1st dose: PPAQ3 (Questions 12-14; completed while patient is in clinic)
- 120 (± 10) minutes after 1st dose: VAS, Dry Mouth Relief Questionnaire (DMRQ), and PPAQ3 (Questions 12-14; completed while patient is in clinic)
- 240 (± 10) minutes after 1st dose: PPAQ3 (Questions 12-14); and PPUQ (**completed while patient is in clinic**)

Other Assessments/Schedule of Events that must be completed during Visit 7 include:

- Collect the patient diary from the patient
- Review any changes in concomitant medications
- Review any side effects/adverse events and resolve if appropriate

After all assessments are completed for Visit 7, the second treatment phase will be considered complete and the subject's participation in the study will be complete.

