9.9 Washout Period

Patients will be required to undergo a washout period twice during the study. The first washout period should occur after the subject signs consent and will last until the baseline visit (Visit 2). The second washout period will start after the end of Visit 4 and last until the beginning of Visit 5. A washout period is necessary to ensure patients proceed to a new treatment period without carrying over any residual effects from previous treatment. During the washout period patients will be instructed *not* to use any over the counter or prescription products for dry mouth. Patients will be allowed to only use water to rinse their mouth during the washout period. If a patient uses any type of oral rinse to treat dry mouth during the washout period it will be considered a protocol deviation.

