12 SAFETY CONSIDERATIONS

12.1 Investigator Responsibilities

The Investigator is responsible for identifying adverse events throughout the study and follow-up period. An adverse event can occur at any time during the conduct of the study, in any phase of the study or after the study is completed. An adverse event can be identified by the Investigator or reported by the patient.

Note: The Federal Privacy Rule (HIPAA) specifically permits the use and disclosure of protected health information "without written authorization of the individual" when used for public health

activities such as reporting adverse events, tracking FDA-related products, enabling recalls, repairs, replacements, lookbacks, or conducting post-market surveillance [45 CFR 164.512]. This use and disclosure is patient to the *minimum necessary* standard, i.e. “the minimum necessary to accomplish the intended use, disclosure, or request” [45 CFR 164.502].

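### Protocol 12.2 collects only treatment-emergent adverse events, an undefined term: first-washout events fall outside it, anticipated sensations have no pre-dose record, and the second product has about 4 hours' observation after its last dose

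*Protocol*

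**What the plan says.** Protocol 12.2 defines an adverse event broadly, as "any undesirable clinical occurrence in a patient, whether or not it is considered to be device- or drug-related". The same section then sets two limits on collection, one on its end and one on its scope: "Adverse events will be collected until the subject has exited/withdrawn from the study. Only treatment-emergent adverse event will be collected and reported". Neither the protocol nor the SAP defines treatment-emergent.

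Protocol 12.1 is wider: "The Investigator is responsible for identifying adverse events throughout the study and follow-up period". It adds that an event can arise in any phase, or after completion. Section 12.3 opens more narrowly than either, with the investigator recording device-related events on the form, and then speaks of reporting adverse events generally.

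The schedule bears on this as follows.

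- **Start.** Patients are enrolled at consent (8.2). The first washout runs from consent to Visit 2 and allows only water as a rinse, with no dry-mouth products (9.9). Table 1 marks adverse events at Visits 2 to 7, not Visit 1. The diary starts at Visit 2 (9.10).
- **End.** After the Visit 7 assessments, the last at 240 minutes after dosing, the subject's "participation in the study will be complete" (section 9.8). The diary is collected at that visit and no later contact is scheduled.
- **Analysis.** SAP 5.8 reports adverse events for the intent-to-treat set, by product and period. SAP 5.2 requires at least one dose for that set.

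**The concern.** Evaluating the clinical safety of MucoPEG is a secondary objective, and 12.2 makes adverse event incidence its principal measure. Three things weaken that measure.

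1. The first washout is imposed by the study: it withdraws whatever dry-mouth product the patient was using. An event it provokes comes before any dose, so 12.2 does not bring it in as an adverse event. If the patient leaves before dosing, the SAP safety tables do not include them either.
2. Section 12.2 anticipates numbness, burning, tingling and taste alteration. The background section says "Mouth dryness is commonly associated with other symptoms such as taste disturbances, bad breath and painful mouth ulcers". Without a pre-dose record of these sensations, a symptom the patient already had can be entered as a reaction to whichever product is in use.
3. A reaction that starts after the last dose has a reasonable chance of being noticed if the product came first, and almost none if it came second.

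**Working it through.** **Stated duration.** The protocol gives about 42 days per participant (8.1, 8.5). First washout (Table 1) plus Visit 7 at Day 35: 7 + 35 = 42. The figure is reproduced, with a range of 40 to 44 from the ±2-day window on Visit 7. Days left after Visit 7: 42 − 42 = 0.

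**First washout outside collection.** Patient-days = patients × days, with 42 patients.

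| Source | Days | Patient-days |
|---|---|---|
| Table 1 footnote (a minimum) | 7 | 42 × 7 = 294 |
| Section 9.3 (1, +2, days after screening) | 1 to 3 | 42 × 1 = 42 to 42 × 3 = 126 |

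The two sources conflict and must be reconciled; the size of the gap depends on which applies. The second washout is not affected, because it follows a first dose.

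**Pre-dose record of the anticipated sensations.** The assessments before the first dose at Visit 2, and before the first dose of the second product at Visit 5, are:

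- VAS: dryness of mouth and of tongue (Appendix A).
- DMI: eight items on dryness, eating, drinking, sucking sweets and sticking of lips or tongue (Appendix C).
- Challacombe examination: observed signs (Appendix E).
- Optional photograph.

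None asks about numbness, burning, tingling or taste. Medical history at Visit 1 might mention them, but without a prompt.

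**Observation after the last in-clinic dose.**

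- First product: Visit 4 (Day 14) to Visit 5 (Day 22) = 8 days. The visit windows alone give 22 − 16 = 6 to 24 − 12 = 12 days.
- Second product: 240 ± 10 minutes, or 3.8 to 4.2 hours.

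**What the end gap could hide.** The documents give no rate for late-onset reactions, so 2% and 5% are assumptions. With 1:1 allocation and no dropout, each product is first for 42 / 2 = 21 patients. The chance of seeing at least one case is 1 − (1 − p)^n, where n is the number of patients observed after their last dose. With no cases seen, the one-sided 95% upper bound is 1 − 0.05^(1/n).

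| | n = 21 (as planned) | n = 42 (if both sequences were observed) |
|---|---|---|
| p = 5% | 1 − 0.95^21 = 66% | 1 − 0.95^42 = 88% |
| p = 2% | 1 − 0.98^21 = 35% | 1 − 0.98^42 = 57% |
| Upper bound, no cases | 13% | 7% |

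These figures apply only to reactions that first appear after the last dose and within about a week of it.

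**The case against.** **Washout harms are not wholly invisible.** A reader might infer that they are never recorded. The documents do not support that. Visit 2 lists a review of side effects and adverse events. Dryness is measured before dosing, changes in medication are noted, and withdrawal reasons go on the eCRF (11.1). Untreated patients are referenced in the final report (19.2), and SAP 5.3 sets the floor for imputed dates at Visit 1. A site may therefore note such an event. What stands is that 12.2 says it will not be collected or reported as an adverse event.

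**The follow-up period in 12.1 may be Visits 3 to 7.** The visit sections call these follow-up visits, and 8.1 says patients are followed for about 42 days. On that reading 12.1 does not require collection after exit, and its remark on events after completion says only when they can occur. This is fair. The conflict that remains is over the phases before first dose, together with an undefined term.

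**Sources that could be over-read.** Section 4.1 reports an association between dry mouth and taste disturbance, not a cause. Section 9.9 says "A washout period is necessary to ensure patients proceed to a new treatment period without carrying over any residual effects from previous treatment"; that concerns carry-over into the next treatment and does not show that harms persist for a week. Section 12.2 expects the anticipated sensations to be mild and temporary.

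**The end gap is narrow.** Reactions during two weeks of twice-daily use are under collection for every patient on the product. The 13% and 7% bounds are not the precision of the overall adverse event rate. A later contact also has a drawback: product use is no longer restricted after Visit 7, so events could be credited to the wrong product. This makes the contact optional.

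**Conclusion.** The point holds in a limited form. Section 12.2 states a positive rule that is narrower than 12.1 and rests on a term neither document defines. Taking its usual meaning, adverse events in the first washout are outside collection and reporting (about 294 patient-days on Table 1, or 42 to 126 on section 9.3). The four anticipated sensations have no prompted pre-dose record, so disease symptoms can be attributed to a product.

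After the last dose, observation is about 8 days for the first product and about 4 hours for the second. A reader might infer that this biases MucoPEG against Biotène. It does not: with 1:1 sequences it falls about equally on both, so the effect is to understate late-onset incidence. The detection figures rest on assumed rates and no dropout.

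**What to change.** - Reconcile protocol 12.1, 12.2, 12.3 and Table 1, and state what the follow-up period is. Reconcile the first-washout length between Table 1 and section 9.3.
- Record adverse events on the existing form from signed consent, flagged as before or after first dose.
- At Visits 2 and 5, before dosing, record whether each sensation listed in 12.2 is already present, and define treatment-emergent against that record.
- Keep the SAP 5.8 product tables to treatment-emergent events. List pre-dose events separately, including those in patients never dosed.
- Either add a brief adverse event contact after Visit 7, recording the products used since, or state in the report that late-onset reactions to the second product were not observed.

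The cost is a short tick-list at two existing visits, a few more adverse event records, and an amendment to both documents. The optional contact would lengthen the stated participation.

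The version history of SAP 1.1 refers to a locked database. If collection is closed, what remains for this trial is the definition, a separate listing of any pre-dose events already held, and the stated limitations. The collection changes would then apply only to further enrolment or a later study.

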12.3 Recording and Reporting

The Investigator records each device-related adverse event on an Adverse Event eCRF. Each record includes the description, severity, seriousness, date of onset and resolution, relationship to the experimental material, action taken and outcome.

The Investigator must promptly report an adverse device effects/adverse events to the Sponsor using the appropriate eCRF in the EDC system. If the Investigator is not able to report the adverse event or adverse device effect through the EDC system, the Investigator must notify the site monitor or Clinical Study Manager. If the adverse device effect/adverse event is considered by the Investigator to be serious and/or unanticipated, the Investigator must report it to the IRB as soon as possible and within IRB requirements.

A serious AE involving the comparative device is reported to the study monitor and IRB.

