5.8 Safety Analyses

Adverse events (AE) will be reported for the intent-to-treat set. AEs will be tabulated with the number of events and affected patients for each event type and for all types combined. Rates will be reported as the number of patients who experience at least one event during the analysis interval out of the total number of patients with follow-up to the beginning of the analysis interval. Serious adverse events will

Statistical Analysis Plan		Page 17 of 17
Sponsor SunBio Inc.	Study Clinical Evaluation of MucoPEG for Xerostomia	Version 1.1

also be tabulated. The rate of all AEs and SAEs reported in the study will be reported by product and by treatment period.

All AEs and SAEs will also be summarized by relatedness to the products under investigation as described above. Details of such events will also be reported in listing format.

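### Protocol 12.3 gives two different scopes for the Adverse Event eCRF, and under neither does SAP 5.8 have a named field for relatedness to Biotène

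*Protocol*

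**What the plan says.** Protocol 12.2 defines two separate terms. The broad one is: "Adverse event (AE) means any undesirable clinical occurrence in a patient, whether or not it is considered to be device- or drug-related". The narrow one, the device-related adverse event, "is an AE considered by the Investigator to have a reasonable likelihood of being associated with the experimental device or device under study". The same section makes AE incidence the main safety measure. The one explicit limit it sets on collection is timing: events must be treatment-emergent, and they are collected until the patient exits or withdraws.

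Protocol 12.3 opens with "The Investigator records each device-related adverse event on an Adverse Event eCRF" and then lists the content of the record: "Each record includes the description, severity, seriousness, date of onset and resolution, relationship to the experimental material, action taken and outcome". Its second paragraph reads "The Investigator must promptly report an adverse device effects/adverse events to the Sponsor using the appropriate eCRF in the EDC system". It names the comparator once: "A serious AE involving the comparative device is reported to the study monitor and IRB".

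Elsewhere the protocol asks for events without regard to cause. Table 1 schedules adverse events at Visits 2 to 7, the visit sections call for a review of them, and the diary in 9.10 covers whichever product the patient is using.

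SAP 5.8 plans counts of AEs by type and overall in the intent-to-treat set, and rates of all AEs and SAEs by product and treatment period. It adds: "All AEs and SAEs will also be summarized by relatedness to the products under investigation as described above".

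**The concern.** The sentence that tells the investigator what goes on the AE form uses the narrow term, while the main safety measure and the SAP tables rest on the broad one. A site that takes the sentence at its word would judge relatedness first and enter only the events that pass. Patients know which product they are using, and Protocol 15.2 says only that assessors may be blinded, so that judgement could differ between MucoPEG and Biotène.

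Two things are at stake. Unrelated AEs, and perhaps non-serious AEs under Biotène, could be missing from the tables that serve the secondary safety objective. And the relatedness summary is promised for both products, although the record described in 12.3 names a relationship to one material only.

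**Working it through.** The documents give no AE rate or count, so there is no figure to reproduce. The check sets the texts side by side.

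**Step 1: which events go on the form.**
- 12.3, opening sentence: device-related AEs, on the Adverse Event eCRF.
- 12.3, second paragraph: device effects and AEs, on the appropriate eCRF. The form is not named.
- 12.2: AEs whatever their cause, limited to treatment-emergent ones.
- SAP 5.8: all AEs and SAEs.

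The last three agree with each other and the first is narrower. Because 12.2 defines AE and device-related AE separately, naming both in the second paragraph of 12.3 brings in unrelated events. One section therefore gives two scopes, and the narrow one sits in the only sentence that names the AE form.

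**Step 2: what each scope does to the tables.** Let *u* be the share of treatment-emergent AEs that a site judges unrelated and leaves off.
- Events entered = true events × (1 − *u*).
- Broad scope followed: *u* = 0, and the all-AE counts by product and period can be produced.
- Narrow scope followed: *u* is the whole unrelated share, the unrelated rows are empty, and the event count is too low by the fraction *u*.
- Between products, the reported ratio of event counts, MucoPEG to Biotène, equals the true ratio × (1 − *u*M)/(1 − *u*B), where *u*M and *u*B are the shares left off under each product. It is undistorted only if the two shares are equal.

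The documents do not give *u*, which could lie anywhere from 0 to 1. The rates in SAP 5.8 count patients with at least one event, so they fall by no simple multiple of *u*: a patient with one related and one unrelated event is still counted.

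**Step 3: the comparator.**
- The related-event definition in 12.2 refers to an event "associated with the experimental device or device under study". Section 6.1.1 uses experimental device for MucoPEG, and the synopsis lists Biotène as the comparative device. Whether device under study takes in Biotène is not stated.
- The causality item in 12.3 names the experimental material and does not mention Biotène.
- The only sentence in 12.3 about comparator events deals with serious ones and sends them to the monitor and IRB.
- SAP 5.8 speaks of products in the plural and refers back to something above, but nothing earlier in the SAP defines relatedness or its categories. If the back-reference means only the method of tabulation, the categories are still missing.

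So even if every AE is entered, relatedness to Biotène has no named field and neither product has defined categories.

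**The case against.** A reader might infer that the protocol forbids recording unrelated AEs, so that the SAP 5.8 table cannot be filled correctly. The documents do not support that. The opening sentence of 12.3 does not say *only*; the limit stated with that word in 12.2 concerns treatment emergence. The second paragraph of 12.3 asks for AEs as well as device effects. A relationship item would also have little to record on a form that admitted related events alone. The eCRF is not among the documents, so what it accepts cannot be checked.

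A reader might also infer that omitted events are lost for good. That goes too far as well: diaries and visit reviews collect events without a relatedness filter, Protocol 13 has eCRFs checked for completeness, and 14.4 bars sites from discarding data. Nor do the documents support any particular figure for the share lost.

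On Biotène, the sentence about serious events sets a reporting route and does not say that non-serious ones go unrecorded. Protocol 15.1 calls both products devices, so the related-event definition can be read to cover both. And SAP 5.8 plans descriptive tables, with no test of AE rates between products.

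All of this stands, and it shows that the broad scope was probably intended. It does not remove the conflict inside 12.3. Diaries and visit reviews bring events to the site's notice, whereas 12.3 governs what is entered, and up to two sites could read it differently. Nor does it supply a field for relatedness to Biotène.

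**Conclusion.** The point holds as an internal inconsistency that should be corrected. Protocol 12.3 conflicts with itself and with 12.2 on which AEs go on the AE eCRF, and its opening sentence is narrower than SAP 5.8 needs. If a site followed that sentence, unrelated AEs and possibly non-serious Biotène AEs would be under-recorded and the descriptive AE rates understated. The documents do not show that any site did so, and the size cannot be derived from them.

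The second part does not depend on which scope sites followed: relatedness to Biotène has no named field in the protocol, and the SAP defines no relatedness categories. This rests on the protocol and SAP text alone; the eCRF or its completion guide may already settle it.

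**What to change.** Reconcile Protocol 12.2, Protocol 12.3 and SAP 5.8:
- Reword the opening sentence of 12.3 so that every treatment-emergent AE, related or not and under either product, is recorded on the AE eCRF. The span is first dose to study exit. It includes the washout between periods and excludes the first washout, which precedes any dose and so falls outside the treatment-emergent limit in 12.2.
- Replace the single causality item with relatedness to MucoPEG and relatedness to Biotène, each in stated categories.
- Put those categories in SAP 5.8 in place of the back-reference, and say which product and period a washout event is counted under.

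New wording cannot change data already collected, because SAP 1.1 (22 May 2023) was written after database lock. So also check diary entries and visit AE reviews against the AE eCRF entries for both products, account for any events found missing, and state in the report which recording rule sites followed.

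The cost is a short text change, slightly more data entry, and one reconciliation check.
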